### **9.2 SETTING**

#### **9.2.1 Definitions**

Study Period: the period of time that includes the exclusion criteria assessment period, baseline, cohort entry date, and follow-up period for the study population. This period is the same for all patients.

The study period will be from 1 January 2008 to 31 March 2018, encompassing date of the earliest data availability to the date of the latest data availability.

Patient Selection Period: the period of time for which patients are eligible to enter the cohort. The earliest date of the patient selection period is 17 November 2015, corresponding to 180-days after US approval date of Stiolto Respimat.

Cohort Entry Date: Date of entry to the initial cohort of Stiolto or Anoro users.

[figure not shown]
Baseline Period: the 180-day period that ends 1 day prior to the cohort entry date used to assess covariate information. The baseline period will vary between patients depending on these dates. The earliest start of the baseline period would be 21 May 2015, the date of Stiolto approval (i.e. 180 days before November 17, 2015).

Follow-Up Period: the period of time between 1 day after the cohort entry date to the earliest occurrence of the outcome (discontinuation of refills), or any censoring criteria (365 days, death, disenrollment, or end of data). Addition of another treatment in addition to index treatment will not count as discontinuation.

For entry into the study population, patients will be required to have 180 days of continuous enrolment with both medical and pharmacy coverage. Data during the baseline period will be used to confirm study eligibility and classification of incident COPD. The follow-up period will be used for capturing first and second maintenance therapies. This is illustrated in **Figure 1**.

Figure 1

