#### **9.3.3 Covariates**

Covariates will be identified based on data recorded within 180 days prior to or on the index date (date of dispensing/initiation of the exposure), unless otherwise specified. If multiple measurements are made in the baseline period, then the most recent measurement will be used.

Covariates will be used to predict propensity scores in later analyses. Absolute and relative frequencies of each covariate will also be reported in Table Shells 1 and 2 (see [Annex 5](#)). Detailed descriptions of the listed covariates can be found in [Annex 3](#) and [4](#).

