**Comorbidities/Symptoms**

- History of All-Cause Hospitalization
- History of Emergency Department Visit
- History of Hospitalization due to Respiratory Condition
- Acute Myocardial Infarction
- Angina Pectoris
- Peripheral Vascular Disease
- Heart Failure
- Hypertension
- Upper Respiratory Infection
- Lower Respiratory Infection
- Cardiac Arrhythmias
- Cerebrovascular Disease
- All Cancers (except nonmelanoma skin cancer)
- Allergic Rhinitis
- Chronic Sinusitis
- Bronchiectasis
- Pneumonia
- Chronic Bronchitis
- Exertional Breathlessness
- Anxiety
- Dementia
- Depression
- Osteoporosis
- Charlson Deyo Comorbidity Index
- Acute Liver Injury or Failure
- Chronic Kidney Disease (without ESRD)
- End Stage Renal Disease
- Rheumatic Disease
- Peptic Ulcer Disease
- Gastroesophageal Reflux Disease
- Type 1 Diabetes Mellitus
- Type 2 Diabetes Mellitus
- HIV/AIDS
- Hemiplegia or Paraplegia

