#### 9.7.1.1 Descriptive Analysis

All variables specified in [section 9.3.3](#) will be reported. For demographic and lifestyle variables, the value recorded on the cohort entry date will be reported, otherwise the most recent known value will be reported. Presence of comorbidities and use of concomitant medication use will be determined based whether they ever occurred within the 180-day baseline period preceding the index date. Differences in the confounder distributions were inspected for successful confounder balance of measured characteristics.

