Acute Myocardial Infarction	
1 Inpatient or 1 Outpatient
 
Diagnosis Code (Position 1), ICD-9 is any of: { “410”, “410.0”, “410.00”, “410.01”, “410.1”, “410.10”, “410.11”, “410.2”, “410.20”, “410.21”, “410.3”, “410.30”, “410.31”, “410.4”, “410.40”, “410.41”, “410.5”, “410.50”, “410.51”, “410.6”, “410.60”, “410.61”, “410.7”, “410.70”, “410.71”, “410.8”, “410.80”, “410.81”, “410.9”, “410.90”, “410.91” }
 
Diagnosis Code (Principal), ICD-10 is any of: { “I21.09”, “I21.11”, “I21.19”, “I21.29”, “I21.3”, “I21.4”, “I22.0”, “I22.1”, “I22.2”, “I22.8”, “I22.9” }

Angina Pectoris	
1 Inpatient or 2 Outpatient (30 – 365 days apart)
 
Diagnosis Code (Any Position), ICD-9 is any of: { “413”, “413.0”, “413.1”, “413.9” }
 
Diagnosis Code (Any Position), ICD-10 is any of: { “I20.1”, “I20.8”, “I20.9” }

Peripheral Vascular Disease	
1 Inpatient or 2 Outpatient (30 – 365 days apart)
 
Diagnosis Code (Any Position), ICD-9 is any of: { “440”, “440.0”, “440.1”, “440.2”, “440.20”, “440.21”, “440.22”, “440.23”, “440.24”, “440.29”, “440.3”, “440.30”, “440.31”, “440.32”, “440.4”, “440.8”, “440.9”, “441”, “441.0”, “441.00”, “441.01”, “441.02”, “441.03”, “441.1”, “441.2”, “441.3”, “441.4”, “441.5”, “441.6”, “441.7”, “441.9”, “442”, “442.0”, “442.1”, “442.2”, “442.3”, “442.8”, “442.81”, “442.82”, “442.83”, “442.84”, “442.89”, “442.9”, “443.1”, “443.2”, “443.21”, “443.22”, “443.23”, “443.24”, “443.29”, “443.8”, “443.81”, “443.82”, “443.89”, “443.9”, “447.1”, “785.4”, “38.13”, “38.14”, “38.16”, “38.18”, “38.33”, “38.34”, “38.36”, “38.38”, “38.43”, “38.44”, “38.46”, “38.48”, “39.22”, “39.23”, “39.24”, “39.25”, “39.26”, “39.29” }
 
Diagnosis Code (Any Position), ICD-10 is any of: { “I70.0”, “I70.1”, “I70.209”, “I70.219”, “I70.229”, “I70.25”, “I70.269”, “I70.299”, “I70.399”, “I70.499”, “I70.599”, “I70.8”, “I70.90”, “I70.91”, “I70.92”, “I71.00”, “I71.01”, “I71.02”, “I71.03”, “I71.1”, “I71.2”, “I71.3”, “I71.4”, “I71.5”, “I71.6”, “I71.8”, “I71.9”, “I72.0”, “I72.1”, “I72.2”, “I72.3”, “I72.4”, “I72.8”, “I72.9”, “I73.1”, “I73.81”, “I73.89”, “I73.9”, “I77.1”, “I77.71”, “I77.72”, “I77.73”, “I77.74”, “I77.79”, “I79.8”, “I96” }

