Heart Failure	
1 Inpatient
 
Diagnosis Code (Any Position), ICD-9 is any of: { “428”, “428.0”, “428.1”, “428.2”, “428.20”, “428.21”, “428.22”, “428.23”, “428.3”, “428.30”, “428.31”, “428.32”, “428.33”, “428.4”, “428.40”, “428.41”, “428.42”, “428.43”, “428.9” }
 
Diagnosis Code (Any Position), ICD-10 is any of: { “I50”, “I50.9”, “I50.2”, “I50.20”, “I50.21”, “I50.22”, “I50.23”, “I50.3”, “I50.30”, “I50.31”, “I50.32”, “I50.33”, “I50.4”, “I50.40”, “I50.41”, “I50.42”, “I50.43” }

Hypertension	
1 Inpatient or 2 Outpatient (30 – 365 days apart)
 
Diagnosis Code (Any Position), ICD-9 is any of: { “401”, “401.0”, “401.1”, “401.9”, “402”, “402.0”, “402.00”, “402.1”, “402.10”, “402.9”, “402.90”, “403”, “403.0”, “403.00”, “403.01”, “403.1”, “403.10”, “403.11”, “403.9”, “403.90”, “403.91”, “404”, “404.0”, “404.00”, “404.01”, “404.02”, “404.03”, “404.1”, “404.10”, “404.11”, “404.12”, “404.13”, “404.9”, “404.90”, “404.91”, “404.92”, “404.93”, “405”, “405.0”, “405.01”, “405.09”, “405.1”, “405.11”, “405.19”, “405.9”, “405.91”, “405.99” }
 
Diagnosis Code (Any Position), ICD-10 is any of: { “I10”, “I11.9”, “I12.0”, “I12.9”, “I13.0”, “I13.10”, “I13.11”, “I13.2”, “I15.0”, “I15.8” }

Upper Respiratory Infection (with no sinusitis)	
1 Inpatient or 2 Outpatient (30 – 365 days apart)
 
Diagnosis Code (Any Position), ICD-9 is any of: { “034”, “034.0”, “034.1”, “460”, “461”, “461.0”, “461.1”, “461.2”, “461.3”, “461.8”, “461.9”, “462”, “463”, “464”, “464.0”, “464.00”, “464.01”, “464.1”, “464.10”, “464.11”, “464.2”, “464.20”, “464.21”, “464.3”, “464.30”, “464.31”, “464.4”, “464.5”, “464.50”, “464.51”, “465”, “465.0”, “465.8”, “465.9”, “487”, “487.1”, “487.8” }
 
Diagnosis Code (Any Position), ICD-10 is any of: { “J03.00”, “J03.01”, “A38”, “A38.8”, “A38.9”, “J00”, “J01”, “J01.9”, “J01.90”, “J01.8”, “J01.80”, “J01.0”, “J01.00”, “J01.01”, “J32.0”, “J01.1”, “J01.10”, “J01.11”, “J32.1”, “J01.2”, “J01.20”, “J01.21”, “J32.2”, “J01.3”, “J01.30”, “J01.31”, “J32.3”, “J02”, “J02.8”, “J02.9”, “J04”, “J04.0”, “J05”, “J05.0”, “J04.1”, “J04.10”, “J04.11”, “J04.2”, “J05.1”, “J05.10”, “J05.11”, “J04.3”, “J04.30”, “J04.31”, “J06”, “J06.9”, “J11.89”, “J11.8”, “J11.1”, “J11”, “J10.89”, “J10.8”, “J10.1”, “J10.00”, “J10.0”, “J10”, “J09.X2”, “J09.X9”, }

	“J09.X”, “J09” }

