Lower Respiratory Infection	
1 Inpatient or 2 Outpatient (30 – 365 days apart)
 
Diagnosis Code (Any Position), ICD-9 is any of: { “466”, “466.0”, “466.1”, “466.11”, “466.19” }
 
Diagnosis Code (Any Position), ICD-10 is any of: { “J20.9”, “J21.0”, “J21.8”, “J22” }

Cardiac Arrhythmias	
1 Inpatient or 1 Outpatient
 
Diagnosis Code (Principal), ICD-9 is any of: { “427”, “427.0”, “427.1”, “427.2”, “427.3”, “427.31”, “427.32”, “427.4”, “427.41”, “427.42”, “427.5”, “427.6”, “427.60”, “427.61”, “427.69”, “427.8”, “427.81”, “427.89”, “427.9” }
 
Diagnosis Code (Position 1), ICD-10 is any of: { “I46.9”, “I47.1”, “I47.2”, “I47.9”, “I48.91”, “I48.92”, “I49.01”, “I49.02”, “I49.1”, “I49.3”, “I49.40”, “I49.49”, “I49.5”, “I49.8”, “I49.9”, “R00.1” }

Cerebrovascular Disease	
1 Inpatient
 
Diagnosis Code (Any Position), ICD-9 is any of: { “430”, “431”, “432”, “432.0”, “432.1”, “432.9”, “433”, “433.0”, “433.01”, “433.1”, “433.11”, “433.2”, “433.21”, “433.3”, “433.31”, “433.8”, “433.81”, “433.9”, “433.91”, “434”, “434.0”, “434.01”, “434.1”, “434.11”, “434.9”, “434.90”, “434.91”, “435”, “435.8”, “435.9”, “436” }
 
Diagnosis Code (Any Position), ICD-10 is any of: { “G45”, “G45.8”, “G45.9”, “I60”, “I60.0”, “I60.00”, “I60.01”, “I60.02”, “I60.1”, “I60.10”, “I60.11”, “I60.12”, “I60.2”, “I60.20”, “I60.21”, “I60.22”, “I60.3”, “I60.30”, “I60.31”, “I60.32”, “I60.4”, “I60.5”, “I60.50”, “I60.51”, “I60.52”, “I60.6”, “I60.7”, “I60.8”, “I60.9”, “I61”, “I61.0”, “I61.1”, “I61.2”, “I61.3”, “I61.4”, “I61.5”, “I61.6”, “I61.8”, “I61.9”, “I62”, “I62.0”, “I62.00”, “I62.01”, “I62.02”, “I62.03”, “I62.1”, “I62.9”, “I63”, “I63.0”, “I63.00”, “I63.01”, “I63.011”, “I63.012”, “I63.019”, “I63.02”, “I63.03”, “I63.031”, “I63.032”, “I63.039”, “I63.09”, “I63.1”, “I63.10”, “I63.11”, “I63.111”, “I63.112”, “I63.119”, “I63.12”, “I63.13”, “I63.131”, “I63.132”, “I63.139”, “I63.19”, “I63.2”, “I63.20”, “I63.21”, “I63.211”, “I63.212”, “I63.219”, “I63.22”, “I63.23”, “I63.231”, “I63.232”, “I63.239”, “I63.29”, “I63.3”, “I63.30”, “I63.31”, “I63.311”, “I63.312”, “I63.319”, “I63.32”, “I63.321”, “I63.322”, “I63.329”, “I63.33”, “I63.331”, “I63.332”, “I63.339”, “I63.34”, “I63.341”, “I63.342”, “I63.349”, “I63.39”, “I63.4”, “I63.40”, “I63.41”, “I63.411”, “I63.412”, “I63.419”, “I63.42”, “I63.421”, “I63.422”, “I63.423” }

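### The two-outpatient-claims rule in Annex 4, applied to acute respiratory infections over a 180-day baseline, codes a patient with a single outpatient episode as having had none

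*Combined protocol and SAP*

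**What the plan says.** Annex 4 gives lower respiratory infection, pneumonia and the measure labelled "Upper Respiratory Infection (with no sinusitis") one common rule: "1 Inpatient or 2 Outpatient (30 – 365 days apart"), with the code in any diagnosis position. Hypertension and most other chronic conditions in the annex carry the same rule. No reason is given for using it on acute infections.

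The window is 180 days. Section 9.7.1.1 says comorbidities are "determined based whether they ever occurred within the 180-day baseline period preceding the index date". Section 9.2.1 defines baseline as "the 180-day period that ends 1 day prior to the cohort entry date used to assess covariate information". Section 9.3.3 differs slightly: "Covariates will be identified based on data recorded within 180 days prior to or on the index date".

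All three infections are listed in Section 9.3.3. None is a component of the Charlson-Deyo index as Annex 4 defines it, so none is dropped from the propensity score (Section 9.2.2, Matched Cohort) or from the multivariable models (Section 9.7.1.3). They are also rows in Tables 2 and 3 of Annex 5.

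For some other conditions Annex 4 accepts "1 Inpatient or 1 Outpatient": acute myocardial infarction and cardiac arrhythmias, with the code in the principal or first position, and acute liver injury or failure, with the code in any position.

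**The concern.** Requiring two spaced outpatient claims is a way to confirm a lasting diagnosis and discard rule-out codes. An acute infection usually generates its claims over days or a few weeks. With a 30-day minimum gap, an outpatient-only patient generally needs two separate episodes to qualify. The flag then measures recurrent or hospitalised infection rather than recent infection.

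Two things are at stake. Section 9.12 treats the Section 9.3.3 covariates as hypothesised confounders and relies on matching to control them. If most single episodes are coded as absent, Tables 2 and 3 could show good balance on these rows while real differences in recent outpatient infection go unseen. Separately, describing new users is a secondary objective, and the tabulated infection prevalences would be too low.

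**Working it through.** The documents state no infection rate or capture figure, so there is nothing to reproduce. The check applies the rule to test patterns, then illustrates its sensitivity under stated assumptions.

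**Step 1: the rule on test patterns.**

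| Claims for one patient | Both outpatient claims must be in baseline | One of the two outpatient claims may precede baseline |
|---|---|---|
| One outpatient | not flagged | not flagged |
| Two outpatient, 10 days apart | not flagged | not flagged |
| Two outpatient, 29 days apart | not flagged | not flagged |
| Two outpatient, 30 days apart | flagged | flagged |
| One inpatient | flagged | flagged |
| Outpatient on days 60 and 250 before index | not flagged | flagged |

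The result for a single episode does not depend on the reading. Only the last row does.

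**Step 2: the upper limit.** Two claims inside a 180-day window are at most 179 days apart, or 180 if the index date counts. Under the strict reading, separations of 181 to 365 days cannot occur.

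**Step 3: sensitivity if both claims must be in baseline.** Assume outpatient claims are Poisson with mean m per 180 days and uniform in time, with the same m for every patient. Let r = 30/180 = 1/6. For n claims, P(range ≥ 30 days) = 1 − [n·r^(n−1) − (n−1)·r^n]. For n = 2 this is 1 − (2/6 − 1/36) = 25/36 = 0.694 (0.699 counting whole days), so about 30% of patients with two claims are also missed. The share flagged among patients with any outpatient claim is the sum over n ≥ 2 of e^(−m)·m^n/n! × P(range ≥ 30 days), divided by 1 − e^(−m):

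- m = 0.1: 0.0033 / 0.0952 ≈ 3%
- m = 0.2: 0.0124 / 0.1813 ≈ 7%
- m = 0.4: 0.0446 / 0.3297 ≈ 14%
- m = 0.5: 0.0661 / 0.3935 ≈ 17%
- m = 1.0: 0.2032 / 0.6321 ≈ 32%

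A simulation with 60,000 patients per rate, in which 40% of episodes also produce a follow-up claim within 14 days, gave 3.4%, 7.0% and 13.6% at 0.1, 0.2 and 0.4 episodes. Short-term follow-up claims barely change the answer.

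**Step 4: sensitivity if one of the two claims may precede baseline.** Assume full prior history. A patient with one baseline claim is flagged if at least one other claim lies 30 to 365 days before it, a span of 335 days. The probability is about 1 − exp(−m × 335/180):

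- m = 0.1: 1 − exp(−0.186) ≈ 17%
- m = 0.2: 1 − exp(−0.372) ≈ 31%
- m = 0.4: 1 − exp(−0.744) ≈ 53%

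Simulation of this reading agrees. Because only 180 days of enrolment are required, some patients have less history, and actual capture under this reading would lie between Steps 3 and 4.

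**Step 5: dependence on equal rates.** If infection rates vary between patients (gamma with shape 0.5, an assumption), the strict reading gives about 10%, 18% and 28% at mean rates of 0.1, 0.2 and 0.4.

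**The case against.** The strongest reply concerns consequence. Every patient starts a fixed LAMA/LABA combination. A recent infection that prompts starting the class confounds the comparison only if it also shifts the choice between the two products, and the documents give no reason to think it does. Oral antibiotics, oral corticosteroids, emergency visits (which in Annex 4 include urgent care), respiratory hospitalisation and chest X-ray are all covariates and would often register a treated episode. A reader might infer that the adjustment is nearly useless or that the hazard ratio is biased; the documents support neither. This part of the objection stands.

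A second reply is that the low capture figures depend on one reading. A reader might infer that the 365-day limit can never operate. That follows only if both claims must fall inside the baseline. Sections 9.3.3 and 9.7.1.1 read that way, but no passage says so outright, and a 365-day limit makes more sense if a claim dated before baseline may support one inside it. This also stands, and it is why two ranges are given. It does not rescue the single episode, which is missed under both readings.

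A third reply is that a reader might take a one-claim rule in any position to be the annex's settled practice for acute events. It is not: myocardial infarction and arrhythmia require the principal or first position, and only acute liver injury accepts any position. That shapes the fix.

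Finally, Section 9.8 says some algorithms draw on pulmonology input and that validated ones are used when available, so the rule could be a deliberate preference for specificity. The annex does not say so for these three measures.

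**Conclusion.** The definitional problem holds under either reading of the look-back. A single outpatient episode of upper respiratory infection, lower respiratory infection or pneumonia is coded as no infection unless a claim for it recurs 30 or more days later. Inpatient, recurrent and late-recoded episodes are captured.

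Sensitivity for outpatient infection is low: about 3–14% if both claims must fall in baseline and about 17–53% if one of them may precede it. These ranges rest on assumed rates of 0.1 to 0.4 episodes per 180 days, equal across patients, and leave out inpatient capture. Higher or more variable rates raise them.

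The consequence is weak adjustment for recent outpatient infection by these three variables and an understated prevalence in Table 2. It does not extend to a demonstrated bias in the primary hazard ratio, whose direction and size cannot be derived from the documents. The change is worth making because the defect is clear and cheap to correct.

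**What to change.** In Annex 4, define upper respiratory infection, lower respiratory infection and pneumonia as one inpatient claim or one outpatient claim in the baseline period, with the outpatient code in the principal or first position, as for acute myocardial infarction. The position requirement limits rule-out claims.

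For the conditions that keep the two-claim rule, state whether the first outpatient claim may precede the 180-day baseline, since the 365-day limit cannot be reached inside it. At the same time, reconcile Section 9.3.3, which counts the index date, with Sections 9.2.1 and 9.7.1.1, which do not.

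The cost is three definition lines and one clarifying sentence, plus the date reconciliation. Section 9.8 allows measure definitions to change where scientifically sensible, with the change recorded in an amendment. The small remaining downside is that some rule-out claims will be counted as infections.

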## Study timeline for the Primary Study Population

## 9.2.2 Study population

The pre-matched study cohort will consist of patients initiating Olodaterol/Tiotropium Bromide or Umeclidinium/Vilanterol between 17 November 2015 and 31 March 2018.

The following exclusion criteria will then be applied:

Aged <40 years.

Enrolment with medical and pharmacy coverage prior to the cohort entry < 180 days.

Never had COPD diagnosis on the cohort entry date or prior to cohort entry.

A record for dispensed Olodaterol/Tiotropium Bromide delivered with Respimat inhalator or Umeclidinium/Vilanterol delivered with the Ellipta Inhaler during the 180-day baseline prior to cohort entry.

[figure not shown]
Diagnosis of asthma any time prior to cohort entry.

Diagnosis of lung cancer any time prior to cohort entry.

Diagnosis of lung transplant any time prior to cohort entry.

Figure 2

Below depicts the flow diagram of patients.

Diagnosis of COPD (ICD-9: 491.\*, 492.\*, 496.\*; ICD-10: J41.0, J41.1, J41.8, J42.\*, J43.0, J43.1, J43.2, J43.8, J43.9, J44.0, J44.1, J44.9) will be defined as the presence of an inpatient or outpatient claim.

Diagnosis of asthma (ICD-9: 493.\*; ICD-10: J45, J45.20, J45.21, J45.22, J45.90\*, J45.99\*) will be defined as either 1 inpatient claim or 2 outpatient events 30-365 days apart.

Diagnosis of lung cancer (ICD-9: 162.2, 162.3, 162.4, 162.5, 162.8, 162.9, 231.2; ICD-10: C34.00, C34.01, C34.02, C34.10, C34.11, C34.12, C34.2, C34.30, C34.31, C34.32, C34.80, C34.81, C34.82, C34.90, C34.91, C34.92, C7A.090, D02.20, D02.21, D02.22, Z85.118) will be defined as either 1 inpatient claim or 2 outpatient events 30-365 days apart.

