History of Hospitalization due to Respiratory Condition	1 Inpatient 
Diagnosis Code (Principal), ICD-9 is any of: { "415.1", "415.11", "415.12", "415.13", "415.19", "465", "465.0", "465.8", "465.9", "466", "466.0", "466.1", "466.11", "466.19", "480.0", "480.1", "480.2", "480.3", "480.8", "480.9", "481", "482.0", "482.1", "482.2", "482.30", "482.31", "482.32", "482.39", "482.40", "482.41", "482.42", "483.0", "483.1", "483.8", "484.1", "484.3", "484.5", "484.6", "484.7", "484.8", "486", "487.0", "488.01", "488.11", "488.81", "490", "491", "491.0", "491.1", "491.2", "491.20", "491.21", "491.22", "491.8", "491.9", "492.0", "492.8", "493.0", "493.00", "493.01", "493.02", "493.1", "493.10", "493.11", "493.12", "496", "515", "516.3", "516.30", "516.31", "516.32", "516.8", "516.9", "518.81", "518.83", "518.84" }
 
Diagnosis Code (Principal), ICD-10 is any of: { "A01.03", "A02.22", "A37.01", "A37.11", "A37.81", "A37.91", "A40.3", "A50.04", "A54.84", "B01.2", "B05.2", "B06.81", "B77.81", "B95.3", "B96.0", "B96.1", "I26.9", "I26.90", "I26.92", "I26.99", "J06", "J06.0", "J06.9", "J09.X1", "J09.X2", "J10.0", "J10.00", "J10.01", "J10.08", "J10.1", "J11.0", "J11.00", "J11.08", "J11.1", "J12", "J12.0", "J12.1", "J12.2", "J12.3", "J12.8", "J12.81", "J12.89", "J12.9", "J13", "J14", "J15", "J15.0", "J15.1", "J15.2", "J15.20", "J15.21", "J15.211", "J15.212", "J15.29", "J15.3", "J15.4", "J15.5", "J15.6", "J15.7", "J15.8", "J15.9", "J16", "J16.0", "J16.8", "J17", "J18", "J18.0", "J18.1", "J18.2", "J18.8", "J18.9", "J20", "J20.0", "J20.1", "J20.2", "J20.3", "J20.4", "J20.5", "J20.6", "J20.7", "J20.8", "J20.9", "J21.0", "J22", "J39", "J39.3", "J39.8", "J39.9", "J40", "J41", "J41.0", "J41.1", "J41.8", "J42", "J43", "J43.0", "J43.1", "J43.2", "J43.8", "J43.9", "J44.0", "J45", "J45.2", "J45.20", "J45.21", "J45.22", "J45.3", "J45.30", "J45.31", "J45.32", "J45.4", "J45.40", "J45.41", "J45.42", "J45.5", "J45.50", "J45.51", "J45.52", "J45.9", "J45.90", "J45.901", "J45.902", "J45.909", "J45.99", "J45.991", "J45.998", "J47.0", "J68.0", "J84.111", "J84.116", "J84.117", "J84.2", }

	“J85.1”, “J96”, “J96.9”, “J96.90”, “J96.91”, “J96.92”, “J96.0”, “J96.00”, “J96.01”, “J96.02”, “J96.1”, “J96.10”, “J96.11”, “J96.12”, “J96.2”, “J96.20”, “J96.21”, “J96.22”, “J98”, “J98.2”, “J98.3”, “J98.8” }

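### The Lower Respiratory Infection covariate omits J44.0, J20.0–J20.8 and (less importantly) 491.22, which the same annex lists for respiratory hospitalisation; a minor under-ascertainment that a code-list edit corrects

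*Combined protocol and SAP*

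**What the plan says.** Annex 4, Lower Respiratory Infection, counts a diagnosis in any position under the rule "1 Inpatient or 2 Outpatient (30 – 365 days apart"). The ICD-9 list is "466”, “466.0”, “466.1”, “466.11”, “466.19" and the ICD-10 list is "J20.9”, “J21.0”, “J21.8”, “J22". Both lists are closed by braces, so they do not look truncated.

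Three other places bear on this.

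- Annex 4, History of Hospitalization due to Respiratory Condition, takes the whole acute bronchitis category, "J20', 'J20.0', 'J20.1', 'J20.2', 'J20.3', 'J20.4', 'J20.5', 'J20.6', 'J20.7', 'J20.8', 'J20.9", and also J44.0 and 491.22. It counts them only as the principal diagnosis of an inpatient claim.
- Section 9.2.2 excludes patients who "Never had COPD diagnosis on the cohort entry date or prior to cohort entry". Its COPD definition includes 491.* in ICD-9 and, in ICD-10, runs to "J43.9, J44.0, J44.1, J44.9) will be defined as the presence of an inpatient or outpatient claim".
- Section 9.2.2 (Matched Cohort) and section 9.7.1.3 put every section 9.3.3 covariate except the Charlson components into the propensity score and into the multivariable Cox and logistic models. Lower Respiratory Infection is one of these covariates. Section 9.12 describes them as hypothesised confounders.

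No reason is given for the narrower list.

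**The concern.** By standard code title (the documents print no labels), J44.0 is COPD with acute lower respiratory infection and 491.22 is obstructive chronic bronchitis with acute bronchitis. In a cohort where every patient has COPD, these are natural codes for a chest infection, and the list built to detect chest infections does not contain them.

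The two halves of the list also differ in scope. The ICD-9 half takes acute bronchitis whole (466.0) and includes 466.19. The ICD-10 half keeps only J20.9 from J20, and only J21.0 and J21.8 from J21.

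Recent chest infection plausibly relates both to the choice of inhaler and to stopping it. A patient whose infection is coded only in the omitted ways is matched as infection-free. Table 2 then understates infection, and its standardised difference cannot show the problem because it is computed on the same incomplete flag.

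**Working it through.** **Step 1: compare the code lists.** This covers J20–J22, J44.0, 466 and 491.22.

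| Code | Lower Respiratory Infection | Respiratory hospitalisation (inpatient, principal) | COPD definition, 9.2.2 |
|---|---|---|---|
| J44.0 | no | yes | yes |
| J20, J20.0–J20.8 | no | yes | no |
| J20.9, J21.0, J22 | yes | yes | no |
| J21.8 | yes | no | no |
| 466 codes | yes (5) | yes (the same 5) | no |
| 491.22 | no | yes | yes, under 491.* |

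Of J44.0 and J20.0–J20.8, 0 of 10 codes are in the Lower Respiratory Infection list; for 491.22 it is 0 of 1.

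**Step 2: where else could an outpatient claim register?**

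- J44.0 is not in the Pneumonia list, nor in the Chronic Bronchitis list, whose ICD-10 codes are J41 and J42 only.
- J44.0 can add the COPD point of the Charlson-Deyo index, taking COPD there as defined in section 9.2.2.
- Any claim from a hospital emergency room or urgent care facility sets the emergency department flag.
- 491.22 is in the Chronic Bronchitis list, so it counts there, subject to that list's claim rule.
- A claim that also carries J20.9 or J22 is captured, because any position counts.

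What is lost is the infection-specific information on outpatient claims carrying only J44.0 or J20.0–J20.8.

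**Step 3: weight of 491.22.** Assume US coding moved to ICD-10 on 1 October 2015 (not in the documents). The last entry date with any ICD-9 day in its baseline is 30 September 2015 + 180 days = 28 March 2016. From 17 November 2015 that is 133 of 866 selection days (15%), and only part of those baselines is ICD-9. So 491.22 matters less than the ICD-10 codes.

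**Step 4: size.** The plan has no figure to reproduce. Assumptions: true infection prevalence p = 10–20%; 20–50% of infections coded only in an omitted way, so flag sensitivity s = 0.8–0.5 with specificity 1; true imbalance between arms d = 3–5 points; hazard ratio of infection for discontinuation 1.2–1.5; 60% of patients with an event; full 1:2 matching.

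- Infections coded only in an omitted way: 14,751 × 0.10 × 0.20 = 295, to 14,751 × 0.20 × 0.50 = 1,475.
- Standard error of the log hazard ratio: events 3,889 × 0.6 = 2,333 and 7,778 × 0.6 = 4,667; √(1/2,333 + 1/4,667) = 0.025.
- Shift with no infection flag at all: ln{[1 + (p + d)(HR − 1)] / [1 + p(HR − 1)]}. At p = 0.15 this is 0.006 (d = 0.03, HR = 1.2) to 0.023 (d = 0.05, HR = 1.5), or 0.2–0.9 standard errors.
- Share of imbalance left after the incomplete flag is balanced: (1 − s)/(1 − sp). For s = 0.8 this is 0.2/0.92 = 0.22 to 0.2/0.84 = 0.24; for s = 0.5 it is 0.5/0.95 = 0.53 to 0.5/0.90 = 0.56.
- Shift attributable to the omission, replacing d by the residual imbalance:
  - smallest: p = 0.10, s = 0.8, residual 0.03 × 0.217 = 0.0065, HR = 1.2, giving 0.0013;
  - largest: p = 0.20, s = 0.5, residual 0.05 × 0.556 = 0.0278, HR = 1.5, giving 0.01255.

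That is about 0.001–0.013, or 0.05–0.5 standard errors.

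**The case against.** The strongest case against is that this is one incompletely ascertained binary flag among many. Oral corticosteroids, oral antibiotics, emergency visits, hospitalisation, pneumonia and chest X-ray are also balanced and carry much of the same information. Inpatient principal J44.0, 491.22 and J20.x already set the respiratory-hospitalisation flag. Section 9.12 plans medical review of code lists before implementation, and section 9.8 allows definitions to be modified. All of this stands and keeps the point minor. It does not remove the point, because the list as written is inconsistent with its neighbour and the planned review is the natural place to correct it.

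Three stronger readings are tempting, and the documents do not support them.

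- A reader might infer that an outpatient J44.0 claim leaves no trace in the covariates. It can add the Charlson COPD point, and the index itself is modelled even though its components are not. It may also set the emergency department flag.
- A reader might take 295–1,475 as the number the edit would recover. The requirement of one inpatient or two outpatient claims 30–365 days apart stays in force within a 180-day baseline, so a patient with a single outpatient J44.0 claim remains negative. Any-position matching also already captures some of these claims.
- A reader might quote a shift approaching one standard error. That figure (0.023) treats the infection flag as absent, whereas the omission leaves only the residual imbalance.

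**Conclusion.** The omission is confirmed code by code and is an internal inconsistency of Annex 4. Its consequence is under-ascertainment of one declared confounder that enters the propensity score, both multivariable models and the balance tables. Outcome definition and cohort entry are not affected.

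On the assumptions above, the remaining bias is at most about half a standard error of the log hazard ratio before the correlated covariates absorb part of it. It is unlikely to reverse the primary conclusion. The size rests on assumed prevalence, coding shares, imbalance and effect, none of which the documents supply; in particular, nothing shows how often J44.0 or J20.0–J20.8 appears without J20.9 or J22. Severity is minor.

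**What to change.** In Annex 4, Lower Respiratory Infection, add J44.0 and 491.22, replace J20.9 with J20.*, and replace J21.0 and J21.8 with J21.*. Document the change by protocol amendment, as section 9.8 requires. Use the corrected flag in the propensity score, the multivariable Cox and logistic models, and Table 2. If the narrower list was intended, state why.

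The cost is a code-list edit and a refit on claims already held. Some patients will be positive on both this flag and respiratory hospitalisation, which does no material harm. The edit leaves the claim-count rule untouched; that is a separate matter, and changing it would not recover the omitted codes.

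A baseline outpatient exacerbation flag (J44.1 or 491.21) could be built in the same pass. It is an optional new covariate, not a correction of this list.
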